### **Serious Adverse Events**

All SAEs that have not resolved by the end of the study, or that have not resolved upon the participant’s discontinuation from the study, must be followed until any of the following occurs:

- The event resolves.
- The event stabilizes.
- The event returns to baseline, if a baseline value/status is available.
- The event can be attributed to agents other than the study intervention or to factors unrelated to study conduct.
- It becomes unlikely that any additional information can be obtained (participant or health care practitioner refusal to provide additional information, lost to follow-up after demonstration of due diligence with follow-up efforts).

Any event requiring hospitalization (or prolongation of hospitalization) that occurs during participation in the study must be reported as an SAE, except hospitalizations for the following:

- Hospitalizations not intended to treat an acute illness or AE (e.g., social reasons such as pending placement in long-term care facility)
- Surgery or procedure planned before entry into the study (must be documented in the eCRF)

Note: Hospitalizations that were planned before the signing of the ICF, and where the underlying condition for which the hospitalization was planned has not worsened, will not be considered SAEs. Any AE that results in a prolongation of the originally planned hospitalization is to be reported as a new SAE.

The cause of death of a participant in a study within 12 weeks of the last dose of study intervention, whether or not the event is expected or associated with the study intervention, is considered an SAE.

Information regarding SAEs will be transmitted to the Sponsor or designee using an SAE reporting form, which must be completed and signed by a physician from the study site and transmitted in a

secure manner to the Sponsor or designee within 24 hours. The initial and follow-up reports of an SAE should be made by encrypted email or facsimile (fax). Telephone reporting should be the exception, and the reporter should be asked to complete the appropriate form(s) first.

### **10.5.6. Product Quality Complaint Handling**

#### **Definition**

A PQC is defined as any suspicion of a product defect related to manufacturing, labeling, or packaging, i.e., any dissatisfaction relative to the identity, quality, durability, reliability, or performance of a distributed product, including its labeling, drug delivery system, or package integrity. A PQC may have an impact on the safety and efficacy of the product. In addition, it includes any technical complaints, defined as any complaint that indicates a potential quality issue during manufacturing, packaging, release testing, stability monitoring, dose preparation, storage or distribution of the product or the drug delivery system.

This definition includes any PQC **related to a device constituent in a combination product, including those used in the administration of the study intervention or the comparator. A device deficiency is an inadequacy of a device with respect to its identity, quality, durability, reliability, safety, or performance. Device deficiencies include malfunctions, use errors, and inadequate labeling.**

#### **Procedures**

All initial PQCs must be reported to the Sponsor by the study site personnel within 24 hours after being made aware of the event.

A sample of the suspected product should be maintained under the correct storage conditions until a shipment request is received from the Sponsor.

### **10.5.7. Contacting Sponsor Regarding Safety, Including Product Quality**

The names (and corresponding telephone numbers) of the individuals who must be contacted regarding safety issues, PQC, or questions regarding the study are listed in the Contact Information page(s), which will be provided as a separate document.

## 10.6. Appendix 6: Contraceptive and Barrier Guidance

Participants must follow contraceptive measures as outlined in Section 5.1, Inclusion Criteria. Pregnancy information will be collected and reported as noted in Section 8.3.4, Pregnancy, and Appendix 5, Adverse Events, Serious Adverse Events, Product Quality Complaints, and Other Safety Reporting: Definitions and Procedures for Recording, Evaluating, Follow-up, and Reporting.

### Definitions

#### *Participant of Childbearing Potential*

A woman is considered fertile following menarche and until becoming postmenopausal unless permanently sterile (see below).

#### *Participant Not of Childbearing Potential*

- **Premenarchal**

A premenarchal state is one in which menarche has not yet occurred.

- **Postmenopausal**

A postmenopausal state is defined as no menses for 12 months without an alternative medical cause. A high FSH level ( $>40$  IU/L or mIU/mL) in the postmenopausal range may be used to confirm a postmenopausal state in female participants not using hormonal contraception or hormonal replacement therapy (HRT), however in the absence of 12 months of amenorrhea, a single FSH measurement is insufficient. If there is a question about menopausal status in female participants on HRT, the female participant will be required to use one of the non-estrogen-containing hormonal highly effective contraceptive methods if they wish to continue HRT during the study.

- **Permanently sterile (for the purpose of this study)**

- Permanent sterilization methods include hysterectomy, or bilateral salpingectomy, or bilateral oophorectomy.
- Has congenital abnormalities resulting in sterility.

Note: If the childbearing potential changes after start of the study (e.g., a premenarchal woman experiences menarche) or the risk of pregnancy changes (e.g., a woman who is not heterosexually active becomes active), a woman must begin a highly effective method of contraception, as described in the table below.

If reproductive status is questionable, additional evaluation should be considered.

Contraceptive (birth control) use by men or women must be consistent with local regulations regarding the acceptable methods of contraception for those participating in clinical studies.

Typical use failure rates may differ from those when used consistently and correctly. Use must be consistent with local regulations regarding the use of contraceptive methods for participants in clinical studies.

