### Sex and Contraceptive/Barrier Requirements

7. Before the first administration of study intervention, a participant must be either:
  - a. Not of childbearing potential (Appendix 10.6): premenarchal; postmenopausal (>45 years of age with amenorrhea for at least 12 months, or any age with amenorrhea for at least 6 months and a serum follicle-stimulating hormone [FSH] level >40 IU/L); permanently sterile (e.g., hysterectomy, bilateral salpingectomy, or bilateral oophorectomy); or otherwise, incapable of pregnancy.
  - b. Of childbearing potential and Practicing a highly effective method of contraception (failure rate of <1% per year when used consistently and correctly) prior to receiving study intervention, and agrees to remain on a highly effective method while receiving

study intervention, and for at least 12 weeks after receiving the last administration of study intervention, the end of relevant systemic exposure, consistent with local regulations regarding the use of birth control methods for participants participating in clinical studies.

The investigator must evaluate the potential for contraceptive method failure (e.g., noncompliance, recently initiated) in relationship to the first dose of study intervention. Examples of highly effective methods of contraception are located in Appendix 10.6.

**Note:** If a participant's childbearing potential changes after the start of the study (e.g., a woman who is not heterosexually active becomes active, a premenarchal woman experiences menarche), she must begin practicing a highly effective method of birth control, as described above.

8. A participant of childbearing potential must have a negative highly sensitive serum ( $\beta$ -human chorionic gonadotropin [ $\beta$ -hCG]) pregnancy test at screening and have negative pregnancy tests before receiving study intervention.
9. A participant of childbearing potential must agree not to be pregnant, breastfeeding, or planning to become pregnant while enrolled in this study or within 12 weeks after the last dose of study intervention.
10. A participant of childbearing potential must agree not to donate eggs (ova, oocytes) or freeze for future use for the purposes of assisted reproduction during the study and for at least 12 weeks after receiving the last administration of guselkumab.
11. A male participant must agree not to plan to father a child while enrolled in this study or within 12 weeks after the last dose of study intervention.

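### Inclusion criterion 7a accepts 6 months of amenorrhoea plus one FSH as postmenopausal, which the appendix it cites says is not enough

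*Protocol*

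**What the plan says.** Criterion 7a (Section 5.1) cites Appendix 6 and then gives its own two routes to postmenopausal status. One needs no FSH: ">45 years of age with amenorrhea for at least 12 months". The other uses FSH: "any age with amenorrhea for at least 6 months and a serum follicle-stimulating hormone [FSH] level >40 IU/L". Criterion 7a also has a residual clause for anyone unable to become pregnant for another reason.

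Appendix 6 (Section 10.6) starts from the position that "A woman is considered fertile following menarche and until becoming postmenopausal unless permanently sterile". It then states: "A postmenopausal state is defined as no menses for 12 months without an alternative medical cause". On FSH it says that a value in the postmenopausal range "may be used to confirm a postmenopausal state in female participants not using hormonal contraception or hormonal replacement therapy", but that "in the absence of 12 months of amenorrhea, a single FSH measurement is insufficient".

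The label decides what follows. Criterion 7b requires highly effective contraception before and during treatment and "for at least 12 weeks after receiving the last administration of study intervention". Criterion 8 requires a negative serum test at screening and negative tests before dosing. Footnote j of the Schedule of Activities (Section 1.3) and Section 8.2.5 require a negative test before each administration. All of these apply only to participants of childbearing potential. Appendix 2 lists FSH as a screening test only.

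**The concern.** The operative eligibility criterion accepts the evidence that its own reference calls insufficient. A site that reads 7a alone sees a clear rule and has no reason to raise a question. It would enrol a participant with, say, 7 months of amenorrhoea and one high FSH without contraception or pregnancy tests, while Appendix 6 classes her as fertile. The safeguard at stake is protection against fetal exposure. Sections 7.1 and 8.3.4 require study intervention to stop in pregnancy, so omitted tests could also delay a mandatory action. The protocol is an original version, so no amendment explains the difference.

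**Working it through.** There is no planned figure to reproduce. The check sets the two definitions side by side and then measures how long they can disagree.

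**Step 1: the rules.** Let A be months of amenorrhoea.
- Criterion 7a: postmenopausal if (age >45 and A ≥12) or (any age, A ≥6 and FSH >40 IU/L).
- Appendix 6: postmenopausal if A ≥12 with no alternative medical cause. FSH is confirmatory only, and only in participants off hormonal contraception and HRT. With A <12, one FSH does not suffice.

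**Step 2: classification**, assuming no permanent sterility, no alternative medical cause and no other reason for being unable to conceive.

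| Participant | 7a | Appendix 6 |
|---|---|---|
| Any age, A 6 to <12, FSH >40 | postmenopausal | fertile |
| Age >45, A ≥12 | postmenopausal | postmenopausal |
| Age ≤45, A ≥12, FSH >40 | postmenopausal | postmenopausal |
| Age ≤45, A ≥12, FSH ≤40 or not done | not postmenopausal | postmenopausal |
| A <6, or A 6 to <12 without FSH >40 | not postmenopausal | fertile |

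The first row is the safety-relevant conflict, because there the operative criterion is the looser text. The fourth row differs the other way and is taken up under the objection.

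**Step 3: how long the first-row conflict lasts.** It ends when A reaches 12, or earlier if menses resume and the change is recognised, since the notes in criterion 7 and Appendix 6 then require contraception. One month = 365.25 / 12 / 7 = 4.348 weeks, so the gap from Week 0 = (12 − A at Week 0) × 4.348.
- A = 6 at Week 0: 6 × 4.348 = 26.1 weeks
- A = 6 at a screening visit 4 weeks earlier: 26.1 − 4 = 22.1 weeks
- A = 9 at Week 0: 3 × 4.348 = 13.0 weeks
- A = 11 at Week 0: 1 × 4.348 = 4.3 weeks

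**Step 4: procedures inside the gap.** Dosing visits are Weeks 0, 4, 12, 16, 20, 28, 36 and 44. Section 4.1 states these for the placebo group; the guselkumab interval is redacted, so the same blinded visits are assumed. Urine tests are scheduled every 4 weeks from Week 0 to Week 48 and at Week 56.
- 26.1 weeks: 5 dosing visits (0, 4, 12, 16, 20) and 7 urine tests (Weeks 0 to 24)
- 22.1 weeks: 5 dosing visits and 6 tests
- 13.0 weeks: 3 dosing visits and 4 tests
- 4.3 weeks: 2 dosing visits and 2 tests

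These count procedures that would be skipped for a hypothetical participant. They do not measure pregnancy risk.

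**The case against.** The best defence is that the texts should be read together. Criterion 7a points to Appendix 6, so a site that follows the pointer meets the 12-month rule, the caution on a single FSH, the limit for hormone users and the advice that "If reproductive status is questionable, additional evaluation should be considered". Section 5 requires sponsor consultation whenever eligibility is in question. Read cumulatively, the stricter condition applies and nobody is wrongly exempted. This softens the conflict but does not remove it: both provisions depend on someone noticing a doubt, and 7a read alone creates none. Appendix 6 in turn sends the reader to Section 5.1, but for contraceptive measures rather than definitions. If Section 5.1 did govern, the looser 6-month rule would apply, which is the problem itself.

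A reader might infer something stronger: that the two texts conflict equally in both directions, so that a participant aged 45 or under with 12 months of amenorrhoea and no high FSH could go through the whole study unprotected. The documents do not support giving that equal weight. A site would have to set aside an inclusion criterion, with waivers not allowed, in favour of an appendix that itself points back to Section 5.1. The over-45 condition applies only to the no-FSH route, since the FSH route is open at any age. Failing both postmenopausal routes also does not end the 7a assessment, because the residual clause remains. The fourth row of the table is a wording mismatch worth tidying, not a second safety gap.

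**Conclusion.** The 6-month FSH route in 7a is wrong as written, because it accepts what the cited appendix rejects. Followed literally, it exempts a participant whom Appendix 6 treats as fertile from contraception and pregnancy testing for at most about 26 weeks on study. That maximum rests on exactly 6 months of amenorrhoea at Week 0 and no alternative medical cause.

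The documents give neither the number of such participants, which may be zero, nor a pregnancy risk, so the harm cannot be sized. Nobody is barred from the trial, since a participant who is not exempt can enter under 7b. There is no effect on any analysis or on the sample size. The correction is cheap and concerns participant safety, so it should be made.

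**What to change.** In criterion 7a, change the FSH route to at least 12 months of amenorrhoea without an alternative medical cause, with FSH >40 IU/L, and allow FSH to be used only in participants not on hormonal contraception or HRT. Keep the over-45 condition on the no-FSH route. This alone removes the safety-relevant conflict.

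As a secondary tidy-up, make Appendix 6 match 7a for participants aged 45 or under (12 months plus a confirmatory FSH >40 IU/L) and carry the alternative-cause condition into the over-45 route, so that both places hold one definition. Do not paste the present Appendix 6 sentence into 7a unchanged, because that would lose 7a's stricter rule at 45 or under.

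The cost is a short amendment to two definitions. Any participant with 6 to just under 12 months of amenorrhoea would need contraception and pregnancy tests until 12 months is reached. Participants aged 45 or under who use hormones could no longer qualify through FSH and would enter under 7b unless another part of 7a applies. FSH is already in the screening laboratory list, so no new assay is needed.

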**EXAMPLES OF CONTRACEPTIVESa ALLOWED DURING THE STUDY INCLUDE FOR PARTICIPANTS OF CHILDBEARING POTENTIAL:**
**USER INDEPENDENT**

**Highly Effective Methods That Are User Independent** *Failure rate of <1% per year when used consistently and correctly.*

- Implantable progestogen-only hormone contraception associated with inhibition of ovulation
- Intrauterine device (IUD)
- Intrauterine hormone-releasing system (IUS)
- Tubal closure (e.g., bilateral tubal occlusion, bilateral tubal ligation)
- Azoospermic partner (*vasectomized or due to medical cause*)  
(*Vasectomized partner is a highly effective contraceptive method provided that the partner is the sole sexual partner of the woman of childbearing potential and the absence of sperm has been confirmed. If not, additional highly effective method of contraception should be used. Spermatogenesis cycle is approximately 74 days.*)

**USER DEPENDENT**

**Highly Effective Methods That Are User Dependent** *Failure rate of <1% per year when used consistently and correctly.*

- Combined (estrogen- and progestogen-containing) hormonal contraception associated with inhibition of ovulationb
  - oral
  - intravaginal
  - transdermal
  - injectable
- Progestogen-only hormone contraception associated with inhibition of ovulation
  - oral
  - injectable
- Sexual abstinence  
(*Sexual abstinence is considered a highly effective method only if defined as refraining from heterosexual intercourse during the entire period of risk associated with the study intervention. The reliability of sexual abstinence needs to be evaluated in relation to the duration of the study and the preferred and usual lifestyle of the participant.*)

**NOT ALLOWED AS SOLE METHOD OF CONTRACEPTION DURING THE STUDY FOR PARTICIPANTS OF CHILDBEARING POTENTIAL (not considered to be highly effective - failure rate of  $\geq 1\%$  per year)**

- Progestogen-only oral hormonal contraception where inhibition of ovulation is not the primary mode of action
- Male or female condom with or without spermicide
- Cap, diaphragm, or sponge with spermicide
- A combination of male condom with either cap, diaphragm, or sponge with spermicide (double-barrier methods)
- Periodic abstinence (calendar, symptothermal, post-ovulation methods)
- Withdrawal (coitus-interruptus)
- Spermicides alone
- Lactational amenorrhea method (LAM)

- a) Typical use failure rates may differ from those when used consistently and correctly. Use should be consistent with local regulations regarding the use of contraceptive methods for participants in clinical studies.

[figure not shown]
## 10.7. Appendix 7: Liver Safety: Suggested Actions and Follow-up Assessments

### 10.7A. STOPPING CRITERIA AND INCREASED MONITORING ALGORITHMS

#### Liver Chemistry Stopping Criteria Algorithm

Study intervention will be discontinued for a participant if liver chemistry stopping criteria are met.

#### Phase 3-4 Liver Chemistry Stopping Criteria and Increased Monitoring Algorithm (no preexisting liver disease)

[figure not shown]

Refer to [Appendix 7B](#), Liver Safety Required Actions and Follow-up Assessments

#### Increased Monitoring Algorithm

Study intervention discontinuation or continued participation will be decided based on the monitoring capability and laboratory results as outlined below. Study intervention will be discontinued for a participant if liver chemistry stopping criteria are met.

**Phase 3-4 Liver Chemistry Increased Monitoring Algorithm with Continued Study Intervention for Participants with ALT or AST  $\geq 3 \times \text{ULN}$  but  $< 8 \times \text{ULN}$  (no preexisting liver disease)**

Refer to [Appendix 7B](#): Liver Safety Required Actions and Follow-up Assessments

## B. LIVER SAFETY REQUIRED ACTIONS AND FOLLOW-UP ASSESSMENTS

Phase 3 to 4 liver chemistry stopping criteria are designed to assure participant safety and to evaluate liver event etiology.

### Phase 3 to 4 Liver Chemistry Stopping Criteria and Follow-Up assessments

Liver Chemistry Stopping Criteria	
ALT or AST-absolute	ALT or AST $\geq 8 \times$ ULN
ALT or AST-Increase	ALT or AST $\geq 5 \times$ ULN but $< 8 \times$ ULN persists for $\geq 2$ weeks ALT or AST $\geq 3 \times$ ULN but $< 5 \times$ ULN persists for $\geq 4$ weeks
Bilirubin	ALT or AST $\geq 3 \times$ ULN and total bilirubin $\geq 2 \times$ ULN
INR^2	ALT or AST $\geq 3 \times$ ULN and international normalized ratio (INR) $> 1.5$
Cannot Monitor	ALT or AST $\geq 5 \times$ ULN but $< 8 \times$ ULN and cannot be monitored weekly for $\geq 2$ weeks ALT or AST $\geq 3 \times$ ULN but $< 5 \times$ ULN and cannot be monitored weekly for $\geq 4$ weeks
Symptomatic	ALT or AST $\geq 3 \times$ ULN associated with symptoms (new or worsening) believed to be related to liver injury or hypersensitivity
Suggested Actions, Monitoring, and Follow-up Assessments	

ACTIONS
 
 
• Immediately stop study intervention
 
• Report the event to the Sponsor within 24 hours
 
• Complete the hepatic event form and complete an SAE eCRF if the event also met the criteria for an SAE
 
• Perform follow-up liver chemistry assessments as described in the FOLLOW-UP ASSESSMENTS column
 
• Monitor the participant until liver chemistry test abnormalities resolve, stabilize, or return to baseline (see MONITORING)
 
 
MONITORING
 
If ALT or AST <math>\geq 3 \times</math> ULN AND total bilirubin <math>\geq 2 \times</math> ULN (or at least a doubling of baseline direct bilirubin for known Gilbert's syndrome) or INR <math>> 1.5</math> (if measured):
 
 
• Repeat liver chemistry tests (include ALT, AST, alkaline phosphatase, total bilirubin, direct bilirubin, and INR^6) and perform liver event FOLLOW-UP ASSESSMENTS within 24 hours
 
• Monitor participant twice weekly until liver chemistry test abnormalities resolve, stabilize, or return to baseline
 
	
FOLLOW-UP ASSESSMENTS
 
 
• Viral hepatitis serology
 
• Obtain blood sample for pharmacokinetic (PK) analysis within 1 week of the event of ALT or AST <math>\geq 3 \times</math> ULN.
 
• Obtain serum creatine phosphokinase (CPK), lactate dehydrogenase (LDH), gamma-glutamyl transferase [GGT], and glutamate dehydrogenase [GLDH], and serum albumin
 
• Fractionate bilirubin
 
• Obtain complete blood count with differential to assess eosinophilia
 
• Record the appearance or worsening of clinical symptoms of liver injury, or hypersensitivity, on the CRF as per CRF completion guidelines
 
• Record use of concomitant medications (including acetaminophen, herbal remedies, recreational drugs, and other over-the-counter medications)
 
• Record alcohol use on the hepatic event form
 
 
If ALT or AST <math>\geq 3 \times</math> ULN AND total bilirubin <math>\geq 2 \times</math> ULN (or at least doubling of baseline direct bilirubin if known Gilbert's syndrome) or INR <math>> 1.5</math> (if measured): obtain the following in addition to the assessments listed above:
 
 
• Anti-nuclear antibody, anti-smooth muscle antibody, Type 1 anti-liver kidney microsomal
 



 
• A specialist or hepatology consultation is recommended
 
 
If ALT or AST <math>\geq 3 \times</math> ULN AND total bilirubin <math>< 2 \times</math> ULN and INR <math>\leq 1.5</math> (if measured):
 
 
• Repeat liver chemistry tests (include ALT, AST, alkaline phosphatase, total bilirubin, direct bilirubin, and INR^6) and perform liver chemistry FOLLOW-UP ASSESSMENTS within 24 to 72 hours
 
• Monitor participants weekly until liver chemistry abnormalities resolve, stabilize, or return to baseline
 
 
RESTART
 
 
• Do not restart participant with study intervention unless allowed per protocol and Sponsor approval is granted
 
• If restart is either not allowed per protocol or not granted, permanently discontinue study intervention. The participant may continue in the study for any protocol-specified follow-up assessments
 
	
antibodies, and quantitative total immunoglobulin G or gamma globulins
 
 
• Serum acetaminophen adduct assay, when available, to assess potential acetaminophen (paracetamol) contribution to liver injury in participants with definite or likely acetaminophen use in the preceding week
 
• Liver imaging (ultrasound, magnetic resonance, or computerized tomography) to evaluate liver disease; complete liver Imaging form
 
• Liver biopsy may be considered and discussed with local specialist if available, for instance: 
 
○ In patients when serology raises the possibility of autoimmune hepatitis (AIH)
 
○ In patients when suspected DILI progresses or fails to resolve on withdrawal of study intervention
 
○ In patients with acute or chronic atypical presentation
 
 
 
• If liver biopsy conducted record in eCRF
 

--	--

1. Serum bilirubin fractionation should be performed if testing is available. If serum bilirubin fractionation is not immediately available, discontinue study intervention if ALT or AST  $\geq 3 \times$  ULN **and** total bilirubin  $\geq 2 \times$  ULN. Additionally, if serum bilirubin fractionation testing is unavailable, **record the absence/presence of detectable urinary bilirubin on dipstick** which is indicative of direct bilirubin elevations suggesting liver injury.
2. All events of ALT or AST  $\geq 3 \times$  ULN **and** total bilirubin  $\geq 2 \times$  ULN or ALT or AST  $\geq 3 \times$  ULN **and** INR  $> 1.5$  (if measured), may indicate severe liver injury (**possible ‘Hy’s Law’**) **and must be reported to sponsor in an expedited manner** using the SAE form, even before all other possible causes of liver injury have been excluded. A confirmed Hy's law case must be reported as an SAE. The INR stated threshold value will not apply to participants receiving anticoagulants.
3. New or worsening symptoms believed to be related to liver injury (such as fatigue, nausea, vomiting, right upper quadrant pain or tenderness, or jaundice) or hypersensitivity (such as fever, rash, or eosinophilia).
4. Includes hepatitis A immunoglobulin M (IgM) antibody, HBsAg; hepatitis C RNA, hepatitis C antibody, cytomegalovirus IgM antibody, Epstein-Barr viral capsid antigen IgM antibody (or if unavailable, heterophile antibody or monospot testing), and hepatitis E IgM antibody.
5. PK sample may not be required for participants known to be receiving placebo or non-comparator interventions. Record the date/time of the PK blood sample draw and the date/time of the last dose of study intervention prior to the PK blood sample draw on the eCRF. If the date or time of the last dose is unclear, provide the participant's best approximation. If the date/time of the last dose cannot be approximated OR a PK sample cannot be collected in the time period indicated above, do not obtain a PK sample. Instructions for sample handling and shipping are in the Laboratory Manual.
6. These are included in the Liver Safety kit. Verify laboratory selections with the Laboratory Manual.
7. These are included in the Liver Follow-Up Kit. Verify laboratory selections with the Laboratory Manual.
8. These are included in the DILI kit. Verify laboratory selections with the Laboratory Manual.

A participant who met liver chemistry stopping criteria cannot restart study intervention, unless all of the following conditions are met:

- Sponsor approval **is granted** (as described below).
- Institutional Review Board/Independent Ethics Committee (IRB/IEC) has been informed.
- The participant has been informed of the potential risks and has consented to resume study intervention.

If Sponsor approval to restart/rechallenge the participant with study intervention **is not granted**, then the participant must permanently discontinue study intervention and may continue in the study for protocol-specified follow-up assessments.

